# 8. Outcome measures

### 8.1 Primary Outcome

The primary outcome measure for this study is the change in cognitive function as measured by Trail Making Test Part B (TMT-B). This is measured as the difference in the time taken to complete the test between pre and post-exercise intervention and compared to the control group. Standardized t-scores will be used to interpret the results of this test.

### 8.2 Secondary Outcomes

Secondary outcome measures included here are those which have been shown previously or that we hypothesize to improve as results of exercise. Analysis will include comparisons of both exercise groups both combined and separately to the control group, and pre- to post-intervention changes within and across exercise groups in the following:

• Changes in other measures of cognitive function as measured by the

neuropsychological assessments

- Changes in motor assessments including balance and reaction time to perturbations
- Changes in cardiorespiratory fitness as measured by peak VO2 achieved and time on the treadmill
- Change in fatigue severity as measured in the FSS; other quality of life, physical activity, and sleep quality scales will be used to enhance interpretation of the FSS findings
- Changes in MRI findings, both structural and functional measures; e.g., increases in hippocampal brain volume, or increases in the degree of functional connectivity or fractional anisotropy between brain regions that sub serve motor, cognitive and behavioral functioning.
- Changes in biomarkers

We are also interested in examining relationships among various outcomes (functional, behavioral, structural, mechanistic, etc.) in persons with TBI. Therefore, secondary analyses may include correlations or comparisons of baseline measures within and across the groups. Comparisons of outcome measures including blood biomarkers, brain imaging, neuropsychological and questionnaire data will also be made to a reference healthy volunteer sample that is matched for sex and age within 5 years.

Table 4.	Summary	of t	the	Relevant	Outcome	Variables	for	the	Secondary	Outcome
Measures										

Test/Construct Measured	Relevant outcome variable
Gait Speed	Free and fast walking velocity
Dual Task Performance	Cognitive and motor cost (difference between DT and ST performance)
LOS/Dynamic Balance	Reaction time, maximal excursion
Elliptical Speed (reciprocal coordination)	Free and fast cadence on the elliptical
SOT/3 sensory systems	Equilibrium score for each sensory system
MCT/involuntary reaction time	Mean latency of responses
Adaptation/stability when perturbed	Sway velocity in 2 conditions

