# 9. Statistical Analysis

### 9.1 Analysis of data

The primary analysis is a mixed model (with time as the within-subject factor and exercise group as the between subject factor) analysis of variance (ANOVA) which will be used to determine significant differences in the primary (ANOVA) and secondary outcome variables (MANOVA by outcome category – i.e. motor, cognitive, behavioral, etc – to help control for multiple comparisons) as a result of exercise. Therefore, the data will include the time points immediately pre and post exercise for all subjects. We are interested in both main effects for time and exercise as well as potential interaction effects between exercise group and time.

All subjects completing the protocol and not withdrawing or presenting off study criteria will be included in the analyses. Secondary analyses related to protocol adherence and other aspects of feasibility are anticipated. Estimation of the necessary and sufficient sample size was calculated for a large effect change in the main outcome variable, pre- to post-training change in executive functioning. Significance will be set at p < 0.05.

While we do not anticipate that subjects will improve over time in the absence of exercise, we have included a waitlist control to evaluate this, and we will compare the amount of change over time in the control group versus the exercise group that were not waitlisted using an independent t-test. Also for the exercise group that was not waitlisted, there will be a three month follow up period evaluated to determine whether there is any change compared to the end of the exercise period using paired t-tests.

The change in aerobic capacity and fast elliptical speed will be correlated with changes in the other outcomes measures. Baseline dopamine transmission scores will also be correlated with all motor outcomes using linear regression.

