### 9.2 Power analysis

Based on findings in the pilot study (11-CC-0088) [32], calculations indicate that 20 subjects would be needed to detect a significant difference in the main outcome variable of executive functioning with Trail Making Test B for an  $\alpha = 0.05$  and  $\beta=0.05$ . Therefore, 20 subjects in each of the conditions are expected (total 60 subjects). Attrition is approximately one-third for an exercise training protocol, so we predict recruitment of 80 subjects with non-penetrating TBI to have at least 20 subjects in each condition have completed the second assessment visit.

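### Secondary outcomes are compared through several contrasts in six categories at p < 0.05, with a MANOVA per category that is not stated to gate the contrasts and gives no control across categories

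*Combined protocol and SAP*

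**What the plan says.** Section 8.2 (Secondary Outcomes) commits the analysis to "comparisons of both exercise groups both combined and separately to the control group, and pre- to post-intervention changes within and across exercise groups". The bullets that follow give six categories: other cognitive measures, motor and balance measures, cardiorespiratory fitness, fatigue and related scales, MRI findings, and finally "Changes in biomarkers".

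Section 9.1 (Analysis of data) specifies a mixed-model ANOVA for the primary outcome and a MANOVA by outcome category for the secondary outcomes, the latter "to help control for multiple comparisons". Its category list is open-ended: it names motor, cognitive and behavioural and then trails off. The threshold is one sentence: "Significance will be set at p < 0.05". Section 9.1 also compares change in the waitlist control "versus the exercise group that were not waitlisted using an independent t-test". This test is separate from the MANOVA and is not made conditional on any earlier result.

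Section 2 lists balance, fitness, quality of life and brain changes as secondary objectives, each framed as an effect of exercise intensity. Section 4.5 allows recent assessments from related studies to serve as baseline, partly to limit practice effects.

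**The concern.** Each secondary category can be looked at in at least four between-arm ways: combined exercise versus control, AET versus control, RET versus control, and AET versus RET (if *across* is read that way). Within-arm pre-post changes come on top. No contrast is named as the one that decides a category, and no order or split of alpha is given. A category could be reported as improved on whichever contrast falls below 0.05.

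The category MANOVA deals with having many variables inside one category. It does nothing across the six categories. It limits the contrasts within a category only if they are read after a significant omnibus result, which the plan does not say.

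The within-arm changes are a separate problem. They stand beside the controlled contrasts but have no comparator. For repeated cognitive tests in particular, a significant pre-post change could be practice, and Section 4.5 shows that the investigators expect practice effects. For the primary outcome, Section 2 already anticipates significance in the aerobic arm alone when the arms are analysed separately. One arm significant and the other not is not a test of a difference between arms.

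At stake is what the trial may claim on its secondary objectives. The primary outcome (TMT-B) is not affected.

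**Working it through.** **What the plan states.** It gives no familywise error rate for the secondary outcomes, so there is no figure of its own to reproduce. The check takes the plan's inputs and asks what they imply.

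**Inputs**
- Level per test: 0.05 (Section 9.1). Sidedness is not stated; two-sided is assumed.
- Completers: 20 in each of three arms (Section 9.2).
- Categories: six (Section 8.2).
- Between-arm contrasts per category: four, as listed under the concern.
- One score per category, so the MANOVA is credited with fully solving the problem of many variables inside a category.
- Correlation between categories: not stated. Values of 0, 0.5 and 0.8 are shown. Positive correlation is plausible, since Section 9.1 says "The change in aerobic capacity and fast elliptical speed will be correlated with changes in the other outcomes measures".
- All six categories null.

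**Step 1: one category.** Simulating two-sided t-tests with 20 per arm, at least one of the four contrasts is below 0.05 in 12.9% of trials. The contrasts share arms, so this is below the 1 - 0.95^4 = 18.5% that four independent tests would give. If contrasts are read only after a significant three-arm omnibus test, the figure is 5.0%.

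**Step 2: six independent categories.** The formula is 1 - (1 - p)^6.
- Not gated: 1 - (1 - 0.1289)^6 = 56.3%.
- Gated: 1 - (1 - 0.0502)^6 = 26.6%.

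**Step 3: correlated categories (simulated).**

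| Correlation | Not gated | Gated by three-arm omnibus |
|---|---|---|
| 0 | 56% | 27% |
| 0.5 | 46% | 21% |
| 0.8 | 32% | 14% |

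**Step 4: sensitivity.**
- With 26/27/27 (the accrual plan) instead of 20 per arm, the ungated independent figure is 56.4%, so it hardly depends on sample size.
- If AET versus RET is not counted, three contrasts give 9.8% per category: 1 - (1 - 0.0977)^6 = 46.0% at correlation 0, and 37% at 0.5.
- If only four of the six categories are null, the four-contrast figures at correlation 0.5 are 36% not gated and 16% gated.

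**Step 5: within-arm tests.** Adding pre-post tests for AET, RET and both pooled raises the ungated figure for one category from 12.9% to 18.8%, provided no arm changes at all. If there is a retest gain, these tests detect a real change. The fault is then attributing it to exercise, which an error rate does not measure.

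**The case against.** The strongest reply has four parts.

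1. *Exercise group may be a three-level factor.* Section 9.1 puts exercise group in the model and states an interest in its interaction with time. With three levels, that test is an omnibus over the between-arm contrasts and could serve as a gate. This stands as a possible reading and is why the gated column is shown. But the gate is not written down, and the waitlist t-test lies outside it. Section 9.1 also uses the time points just before and after exercise for all subjects, including waitlisted patients who train later, so a three-arm factor is not certain. Even with the gate, 14-27% remains across categories.

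2. *Six null categories is pessimistic.* This stands. The pilot in Section 1.2.1 reports a gain in peak VO2 of 3.1 ml/kg/min (p = 0.003), and balance gains were seen with RET. Fewer null categories mean a lower risk.

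3. *Secondary outcomes often go without familywise control, and the plan promises none.* This also stands: 0.05 is a per-test threshold. But then the plan should say that these outcomes support no confirmatory claim, and it does not.

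4. *The waitlist is there to show change without exercise.* True, and that is the reason to rest conclusions on the comparison with it rather than on within-arm tests.

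A reader might go further and infer that the plan carries a fixed false-claim rate of about 45%. The documents do not support one number: that value needs a particular correlation or contrast count, no gate, and six null categories. A reader might also infer that retest gain makes a false claim almost certain. The documents give no size for such a gain, and it is not credible for MRI volumes or blood biomarkers. Nor is it right that there is no control at all, since the MANOVA does act within a category.

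**Conclusion.** The point holds. Under the plan as written, several contrasts in each of six secondary categories can be declared at 0.05, with no stated gate and nothing across categories. The chance of at least one false secondary claim is about 32-56% without a gate and about 14-27% with a three-arm omnibus gate. Both ranges assume 20 completers per arm, four between-arm contrasts, six null categories, one test per contrast and category, and a between-category correlation from 0.8 to 0, which is an assumption rather than a figure from the plan. Both fall if some categories truly improve. Separately, the within-arm tests cannot support a statement about exercise, whatever their error rate. This should be corrected because it changes what the secondary objectives can conclude.

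**What to change.** In Sections 8.2 and 9.1:

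1. State that the secondary outcomes are exploratory and support no confirmatory significance claim.
2. Base any statement about an exercise effect on the randomised between-arm comparison of change from baseline to month 3. Use the three-arm group-by-time test for the category as the gate, and open the arm contrasts (combined, AET and RET versus control, and AET versus RET) only when it is significant. Bring the separate waitlist t-test under the same rule for these outcomes.
3. Report within-arm pre-post changes as estimates with confidence intervals, without a test.
4. Fix the list of categories, and say whether *across* means AET versus RET.

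The gate alone leaves 14-27% across six categories, so the exploratory label is still needed.

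The cost is wording only, with no new data or patients. The downside is that fewer secondary results can be called significant.

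Using combined exercise versus control as the only gate, with Holm across categories, is tempting but not advised. If only one regimen helps, at an assumed standardised effect of 0.8, that contrast has about 26-30% power at 0.05 (depending on the variance used) and about 8-11% at the first Holm step (0.05/6 = 0.0083). That arm alone versus control has 69% at 0.05. Such a gate would also sit badly with the exercise-intensity objectives in Section 2.

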#### **Motor Assessment**

#### **Neuropsychological Assessment**

Test scores (and standardized scores) as indicated by the instrument

CNS IRB Protocol Template (2.5.15)

#### Questionnaires

Composite and domain scores as indicated by the instrument.

#### **Physical Performance**

Test/Construct Measured	Relevant outcome variable
CPET	Peak WR, peak HR, time to volitional exhaustion
Pulmonary gas exchange	VO 2 at peak exercise and AT

Imaging

Test/Construct Measured	Relevant outcome variable
Diagnostic MRI Scan	Volume of brain structures
DTI	Tracking of white matter tracts and brain connectivity
BOLD	Regional differences in cerebral blood flow at rest and during hypercapnic challenge indicating cerebral vascular reactivity
fMRI with PASAT	Comparison of active brain regions during a cognitive task

# 9. Statistical Analysis

### 9.1 Analysis of data

The primary analysis is a mixed model (with time as the within-subject factor and exercise group as the between subject factor) analysis of variance (ANOVA) which will be used to determine significant differences in the primary (ANOVA) and secondary outcome variables (MANOVA by outcome category – i.e. motor, cognitive, behavioral, etc – to help control for multiple comparisons) as a result of exercise. Therefore, the data will include the time points immediately pre and post exercise for all subjects. We are interested in both main effects for time and exercise as well as potential interaction effects between exercise group and time.

All subjects completing the protocol and not withdrawing or presenting off study criteria will be included in the analyses. Secondary analyses related to protocol adherence and other aspects of feasibility are anticipated. Estimation of the necessary and sufficient sample size was calculated for a large effect change in the main outcome variable, pre- to post-training change in executive functioning. Significance will be set at p < 0.05.

While we do not anticipate that subjects will improve over time in the absence of exercise, we have included a waitlist control to evaluate this, and we will compare the amount of change over time in the control group versus the exercise group that were not waitlisted using an independent t-test. Also for the exercise group that was not waitlisted, there will be a three month follow up period evaluated to determine whether there is any change compared to the end of the exercise period using paired t-tests.

The change in aerobic capacity and fast elliptical speed will be correlated with changes in the other outcomes measures. Baseline dopamine transmission scores will also be correlated with all motor outcomes using linear regression.

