# Precis

# Objective

The broad objective of this study is to examine the effects of moderate and more intense aerobic exercise as an intervention on cognitive performance, physical functioning and health-related quality of life in patients with chronic (more than 12 months post-injury) traumatic brain injury (TBI). Importantly, structural and biological brain changes will be measured to examine whether functional outcomes are related to exercise-induced adaptations. It is hypothesized that in the chronic phase of persons with TBI, there will be improved: 1) cognitive function, 2) physical fitness and fatigue severity, 3) motor performance and balance, and 4) mood and depressive symptoms, in those that performed the exercise intervention compared to a control group. It is also hypothesized that these functional improvements will be related to exercise intensity, improved cortical connectivity, dopamine transmission gene scores, and blood biomarkers related to neuroand angio-genesis.

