#### Rapid-Resistive Exercise Training (RET)

CNS IRB Protocol Template (2.5.15)

Rapid, reciprocal exercise will be performed using an elliptical trainer, which allows for safe fast speed training. Similar to the previous study (10-CC-0150), this type of training will involve rapid movement and coordination of all four extremities. Emphasis will be placed on increasing speed, however resistance can be increased to keep the level of exercise at a light to moderate intensity. Exercise intensity would not exceed ~ 50% of maximal VO2 (moderate intensity).

The objectives of this study are:

- Primary To evaluate the effects of exercise training intensity on cognitive function in patients with TBI
- Secondary To evaluate the effects of exercise training intensity on balance, physical fitness and quality of life in patients with TBI
- Secondary To evaluate the effects of exercise training intensity on structural and functional changes in the brain of patients with TBI
- Secondary To examine the relationship between cognitive, behavioral, and motor outcomes and brain imaging, biomarker and genetic outcomes or variables
- Secondary To examine structural/functional brain differences, blood biomarkers and a subset of cognitive and self-reported outcomes between patients with TBI and healthy volunteers within the same age range

Since the direct effects of physical exercise are well known, the primary focus here is on the effects of exercise on cognitive function and on brain connectivity. While we anticipate that exercise regardless of intensity will improve cognitive and behavioral outcomes, we anticipate that the effects will be greater for the aerobic training group such that when the results are analyzed separately for each exercise condition, only the aerobic group will demonstrate a significant change in the primary outcome measure. Study outcomes such as brain imaging, blood biomarkers, cognitive performance and selfreported questionnaires in patients with TBI will also be compared to a healthy volunteer sample matched to the TBI cohort for sex and age within 5 years.

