Subjects randomized to the wait-list control will be further randomized to either AET or RET after Assessment Visit 2. In the first 3 months, subjects in the wait-list control will receive no exercise training; however they will be contacted monthly to ensure compliance and to maintain contact (Appendix 10). For subjects initially randomized to either AET or RET, they will no longer follow a formal exercise intervention at NIH following Assessment Visit 2. However, they will be contacted monthly for the next 3 months and asked about their weekly physical activities (Appendix 10).

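### On its natural reading, the primary ANOVA in 9.1 leaves out the waitlist's untreated months and so does not estimate the control-based primary outcome in 8.1

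*Combined protocol and SAP*

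**What the plan says.** Four places bear on what the primary analysis is meant to show.

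- **Section 2, Study objectives.** The only objective labelled primary is "To evaluate the effects of exercise training intensity on cognitive function in patients with TBI". The same section expects that, with the regimens analysed separately, "only the aerobic group will demonstrate a significant change in the primary outcome measure".
- **Precis and section 8.1.** The Precis states the hypotheses as improvement "in those that performed the exercise intervention compared to a control group". Section 8.1 defines the primary outcome as the difference in TMT-B completion time "between pre and post-exercise intervention and compared to the control group".
- **Section 9.1.** The primary analysis is a mixed ANOVA with time within subjects and exercise group between subjects. Both main effects and the interaction are of interest. On the data it says: "Therefore, the data will include the time points immediately pre and post exercise for all subjects". A later paragraph plans a separate comparison of change in the control group "versus the exercise group that were not waitlisted using an independent t-test".
- **Section 9.2.** The sample size is 20 per condition, 60 in all, with 20 in each condition to complete the second assessment visit, at alpha 0.05 and beta 0.05.

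Section 4.4.7 fixes the timing: "Subjects randomized to the wait-list control will be further randomized to either AET or RET after Assessment Visit 2".

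**The concern.** Sections 8.1 and 9.1 do not fit together. The outcome is defined against a control group, but the analysis called primary appears to contain no untreated control observations. The randomised waitlist period is the trial's protection against retest gain, and it is used only in a test with no stated standing.

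At stake is how the trial would be read. If the ANOVA time effect were significant and the waitlist t-test were not, the plan does not say which result answers the question. TMT-B is given at every assessment, and section 4.5 cites practice effects as one reason for reusing recent assessments. A fall in completion time from pre to post could therefore arise without any exercise effect.

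**Working it through.** **1. Which visits enter the ANOVA.** Apply the data sentence in 9.1 to the schedule in 4.1 and 4.4.7.

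| Randomised to | Visit just before exercise | Visit just after exercise | Period left out |
|---|---|---|---|
| AET | baseline | month 3 | months 3 to 6 |
| RET | baseline | month 3 | months 3 to 6 |
| Waitlist | month 3 | month 6 | months 0 to 3, untreated |

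The waitlist's untreated change is outside the model. Giving the group factor a third level for subjects who waited first would not alter this, because that level would still contribute months 3 to 6.

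**2. What each term can show.**

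- *Group main effect:* compares average TMT-B levels between exercise groups, not change.
- *Group-by-time interaction:* compares change under AET with change under RET. This is the intensity objective, and equal practice in both groups cancels. If both regimens help equally, it rejects only at its 5% error rate.
- *Time main effect:* average change over the exercise period. It contains exercise effect plus retest gain, with no untreated comparator. Section 8.1 uses standardised scores for interpretation, but nothing says they correct for repeated testing.

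**3. The plan's own figure of 20.** No numeric effect is given. Section 9.1 speaks only of a large effect on pre-to-post change, so 0.8 SD of change is assumed here, with two-sided alpha.

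- Paired change: n = ((1.960 + 1.645)/0.8)² = 20.3, so 21. The exact paired t-test gives 23. With n = 20, 95% power corresponds to a paired effect of about 0.85.
- Two groups: n per arm = 2 × (3.605/0.8)² = 40.6, so 41. The exact t-test gives 42.

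The stated 20 therefore fits a within-subject test and not a control comparison at the same assumed effect.

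**4. Illustration of the time effect.** Inputs: 60 completers (9.2), made up of 20 AET, 20 RET and 20 waitlist split 10/10; no exercise effect; SD of change set to 1; two-sided 0.05; 58 df. The retest gain g is assumed. If g is equal at every retest, the non-centrality is g × √60. For g = 0.2 this is 0.2 × 7.746 = 1.549, and the non-central t gives 33%. If waitlist subjects gain nothing at their third test, the mean gain is (40g + 20 × 0)/60 = 2g/3. These cases were simulated with 40,000 trials each.

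| Assumed gain (SD of change) | Time effect significant, equal gains | Time effect significant, no gain at third test |
|---|---|---|
| 0.1 | about 12% | about 8% |
| 0.2 | about 33% | about 17% |
| 0.3 | about 63% | about 32% |

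The interaction and the waitlist comparison (20 vs 40) stayed near 5% throughout. These runs included no selective dropout.

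**5. Power if the control contrast becomes primary.** For 20 vs 20 at an assumed d of 0.8, the non-centrality is 0.8 × √(20/2) = 2.53, and power is about 69%. For 95% power with 20 vs 20, d must be about 1.17.

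**The case against.** The strongest reply is that the control comparison is already planned. Section 8.1 ties the primary outcome to it and 9.1 supplies a matching t-test on change. This stands: the contrast is present but unranked, and 9.1 does not say whether AET and RET are pooled in it. A reader might infer that the trial has no control comparison at all. The documents do not support that.

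A reader might also infer that 9.1 assumes away retest gain, from its words "While we do not anticipate that subjects will improve over time in the absence of exercise". The sentence goes on to say that the waitlist was included to evaluate this very point. It is an expectation with a planned randomised check. Section 4.5 does not contradict it: practice effects are mentioned there only in connection with reusing assessments, and no TMT-B gain is given.

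It would also go too far to say that the time effect is the only ANOVA term bearing on efficacy. An interaction favouring AET would be evidence that aerobic training does something beyond RET, and it answers the objective labelled primary. What it cannot do is detect a benefit shared by both regimens.

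The exclusion of untreated data is the natural reading, not a certainty. Section 9.1 says which visits the data will include, and 9.2 counts three conditions of 20 at the second visit, which would suit a three-arm month 0 to 3 analysis. Against that reading, month 3 is not a post-exercise visit for the waitlist.

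Finally, the error rates matter only if the time effect is read as efficacy on its own, and the documents do not say that it will be.

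**Conclusion.** The point holds as a mismatch between the defined primary outcome and the analysis labelled primary. On the natural reading of 9.1, that ANOVA does not estimate TMT-B change compared with control, and the comparison that does has no stated rank. This conclusion needs no assumed retest gain.

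The size of the harm does depend on one. It is small at 0.1 SD of change or less. It becomes material at 0.2 to 0.3 SD, where the time effect is significant in about 33% to 63% of trials with equal gains, or 17% to 32% with none at the third test. These figures are illustrative and assume 60 completers and no exercise effect.

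A reader might also infer that the trial is underpowered for the control comparison. That is not shown: the pilot effect behind 9.2 is not stated, so any shortfall is conditional on the effect assumed.

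**What to change.** Reconcile sections 2, 8.1, 9.1 and 9.2 as follows.

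- State that the month 0 to 3 comparison of the randomised groups, with the waitlist's months 0 to 3 as control, is the primary test of whether exercise works.
- Name one contrast in advance. Whether it pools the regimens or takes one against waitlist is for the investigators to choose to suit their objective.
- Keep the AET versus RET contrast, with its confidence interval, for the intensity objective.
- Keep the pre/post-exercise ANOVA as supportive, and state that its time effect alone is not evidence of efficacy.
- Restate 9.2 for the chosen between-group contrast, with its numeric effect size.

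The data are already to be collected, so the change needs no new visits. It has two costs. The waitlist's crossover data become supportive for efficacy, and the stated power may fall: 20 vs 20 gives about 69% at an assumed d of 0.8, and 95% there would take 41 to 42 per arm, against 20 planned and a ceiling of 80 subjects with TBI. If the pilot effect supports a d of about 1.17 or more, the 95% survives. The investigators hold that figure and should report it.

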This assessment visit will last approximately 8 hours, including time for rest and meals, and may be performed within one day or over the course of several days within a 4 week period. Upon completion of all baseline assessments, patients will be block randomized to one of three groups: 1) a waitlist control, 2) an exercise intervention consisting of exercise at vigorous intensity (Aerobic exercise training group, AET), or 3) an exercise intervention consisting of exercise at moderate intensity (Rapid resistive exercise training group, RET). Both training interventions will be performed 3 times a week for 12 weeks, with a session duration of approximately 1 hour. After 12 weeks, all patients will repeat the same assessments performed at baseline (3 month follow-up). Patients in the control group will then be randomized to either AET or RET, while patients in the exercise training groups will cease their formal supervised exercise training regimen. All patients will return after 12 weeks to perform their final assessment visit (6 month follow-up).

All assessments and training interventions are outpatient visits and will occur at the NIH Clinical Center in the Rehabilitation Medicine Department.

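### Section 9.1 lists several unadjusted 0.05 tests of TMT-B and does not say which one decides the primary question that section 8.1 defines as change compared with control

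*Combined protocol and SAP*

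**What the plan says.** Section 8.1 defines the primary outcome as the "difference in the time taken to complete the test between pre and post-exercise intervention and compared to the control group". That is a between-group comparison of change.

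Section 9.1 makes a mixed-model ANOVA the primary analysis and says of it: "We are interested in both main effects for time and exercise as well as potential interaction effects between exercise group and time". It adds "Significance will be set at p < 0.05". It then describes a comparison of the amount of "change over time in the control group versus the exercise group that were not waitlisted using an independent t-test", introduced to check whether subjects change without exercise. The outcome for that t-test is not named.

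The ANOVA data are described thus: "the data will include the time points immediately pre and post exercise for all subjects". The levels of the exercise-group factor are not given. Section 4.1 says "patients will be block randomized to one of three groups", and waitlist subjects are later randomised to one of the two regimens. The factor could therefore mean the three arms, exercise against waitlist, or aerobic (AET) against rapid-resistive (RET) training with waitlist subjects entered after crossover.

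The one device offered "to help control for multiple comparisons" is a MANOVA by category, and it covers secondary outcomes only. Section 2 also anticipates a result on the primary outcome "when the results are analyzed separately for each exercise condition".

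**The concern.** A reader of 9.1 cannot tell which result would count as a positive trial. Three ANOVA effects and, by inference, a t-test are available for TMT-B at 0.05 each, with no order among them and no adjustment.

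The tests are not interchangeable. Only the interaction (when waitlist is one of the groups) and the t-test estimate the contrast in section 8.1. The time main effect pools the groups, so it has no control. The group main effect averages the pre and post scores, and exercise cannot affect the pre score. At stake is whether an uncontrolled pre-post gain, or a group difference that is not a difference in change, could be reported as the primary exercise effect.

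**Working it through.** **The plan's own figures.** The plan states no family-wise error rate; p < 0.05 per test is all it gives. Section 9.2 gives 20 per condition (60 in total) at alpha 0.05 and beta 0.05, but no TMT-B mean difference or SD, so that figure cannot be reproduced from stated inputs. With d = 0.8 assumed for the large effect mentioned in 9.1, a paired pre-post calculation gives 21 (normal approximation, two-sided). A two-group comparison needs 41-42 per group. The stated 20 is thus close to a within-group calculation and does not show which test the plan was sized for.

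**Inputs.** From the documents: 20 completers per arm, and 0.05 per test. Assumed: two-sided tests, d = 0.8, and pre-post correlation r (none is given; 0.5, 0.7 and 0.9 were tried).

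**Step 1: chance that at least one test is significant under no effect.** If four tests were independent the rate would be 1 − 0.95^4 = 18.5%; for three, 1 − 0.95^3 = 14.3%. The tests are partly correlated, so the rate was simulated (100,000 trials per scenario, no exercise effect, no practice gain):

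| Meaning of exercise group | Any of the four tests < 0.05 |
|---|---|
| Three arms of 20 | 16.4-16.6% |
| AET vs RET, waitlist entered after crossover | 17.1-17.2% |
| Exercise vs waitlist | 13.7-13.9% |

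The ranges are over r. In the last row the interaction F equals the square of the t statistic, so only three tests are distinct. In the three-arm case each test alone rejects in about 5% of null trials. Leaving out the group main effect lowers that row from about 16.5% to about 12.2%. Adding AET-vs-control and RET-vs-control comparisons raises it to about 19%.

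**Step 2: the time main effect when there is a retest gain.** Section 9.1 does not expect change without exercise, but section 4.5 gives avoidance of practice effects as a reason for reusing recent assessments. For a common gain g (in SD units) over 60 subjects, the noncentrality is g / √(2(1 − r)/60). At r = 0.7 the denominator is √(0.6/60) = 0.10.

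| Gain g (assumed) | Noncentrality (df = 57) | Time test rejects | Any of four (three arms, simulated) |
|---|---|---|---|
| 0.1 SD | 1.0 | 17% | 26% |
| 0.2 SD | 2.0 | 50% | 56% |
| 0.3 SD | 3.0 | 84% | 86% |

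No subject benefits from exercise in these trials.

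**Step 3: power of the group main effect against the difference in change.** For one exercise arm against control, n = 20 per arm and a true post-exercise difference d = 0.8:

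- Difference in change: standardised effect d / √(2(1 − r)). At r = 0.7, 0.8/√0.6 = 1.033; noncentrality 1.033 × √10 = 3.27; power 89%.
- Group main effect: standardised effect (d/2) / √((1 + r)/2). At r = 0.7, 0.4/√0.85 = 0.434; noncentrality 0.434 × √10 = 1.37; power 27%.
- At r = 0.5 the standardised effects are 0.80 and 0.462, and power is 69% against 30%.

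A three-arm simulation with d = 0.8 in both exercise arms and r = 0.7 gives 92% for the interaction and 27% for the group effect.

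**The case against.** The plan nowhere says that one significant result out of four counts as success. Section 9.1 only expresses interest in the effects, and section 8.1 points to change compared with control. The t-test is introduced as a check on the no-change assumption. On one natural reading the tests answer different questions: time for exercise, interaction for intensity, the t-test for the assumption. Pooling them into one error rate is then partly convention.

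This stands in part, and it limits what can be said. A reader might infer that the plan carries a 17% chance of a false claim. The documents do not support that: the figure needs an any-of-four rule that is not written, and one reading of the factor leaves only three distinct tests. A reader might also infer that chance baseline imbalance in the group main effect produces the inflation. It does not. Under randomisation that effect rejects at 5%. Baseline difference does account for (1 + r)/2 of its null variance (85% at r = 0.7), but by symmetry so does the post score. The consequence is lost power.

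What the objection does not remove is the gap itself. Section 9.1 contains no rule that excludes such a claim, does not tie 8.1 to a test, and treats both main effects as effects of interest for differences resulting from exercise.

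**Conclusion.** The point holds as a missing decision rule for the primary outcome. If any listed test may support the claim, the false-positive rate is about 14-17%, given two-sided tests, 20 per arm, no practice effect, and TMT-B as the outcome of the t-test (an inference). These are two-sided or omnibus rates; false claims in the favourable direction only would be fewer.

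The larger exposure is the uncontrolled time main effect, whose size depends on an assumed gain and correlation. The group main effect is valid but weak, because averaging in the pre-exercise score halves the treatment signal. Its power disadvantage depends on r and is smaller at lower correlations. This should be corrected before analysis, because neither main effect estimates the outcome that section 8.1 declares.

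**What to change.** In 9.1, name one decisive TMT-B test that matches 8.1: the between-group difference in change from baseline to month 3 among the groups as first randomised. State whether it is pooled exercise against waitlist or a three-arm test, and place the separate AET and RET comparisons after it in a fixed order. Label the time effect, the group main effect, the analysis that includes waitlist subjects' post-crossover data, and all other TMT-B tests as supportive or descriptive.

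No new data are needed, but the change is more than wording. A main effect or an uncontrolled pre-post change can no longer count as primary success, and the waitlist subjects' post-crossover data leave the decisive test.
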